#### 5.3 Statistical methods

#### 5.3.1 Discussion of Analytical Approaches

The statistical analyses will be performed in accordance with Good Pharmacoepidemiology Practice (GPP) guideline / International Conference on Harmonisation (ICH) E9 guideline and will be based on the pooled data from the individual study sites, unless otherwise stated. The Statistical analysis will be performed by Parexel and reviewed by Recordati.

#### 5.3.2 Analysis of the Primary Endpoint

The mean UFC for a participant at any particular visit is collected in the site. If mean UFC is not available at that visit, the mean UFC will be computed based on two or more individual 24hr UFC specimens at that visit. If there are only one individual 24hr UFC specimen available at that visit, then this one individual 24hr UFC specimen will be considered as mean UFC with the acknowledgement of clinical practice in France where one 24 hours UFC can inform on clinical decision.

The primary endpoint is the number and proportion of participants with mUFC ≤ ULN at 12 weeks will be summarized descriptively along with associated 95% CI. The participants who discontinued treatment prior to 12 weeks for any reason or were lost-to-follow up will be considered non-responders for the primary endpoint. The participants who started treatment with osilodrostat less than 12 weeks prior to the end of the abstraction period and are still treated with osilodrostat at the end of the abstraction period will be excluded from the analysis.

Project Document Version No.: 4.0; Document Effective Date: 30 October 2023

CONFIDENTIAL

# RECORDATI AG, Rare Diseases Branch LCI699-RECAG-NI-0596

Statistical Analysis Plan

The primary endpoint will be evaluated also on the modified ITT population, in which participants who had any intervention for any reason or condition that would not allow to have a mean UFC evaluation at 12 weeks will be excluded from the analysis. Participants who discontinued prior to 12 weeks due to safety reasons will be considered non -responders.

The summary statistics will include sample size, frequency, percentages, and 95% CI for proportion.

A participant level listing of participants with mUFC will be provided with UFC, ULN, date of assessment, lost to follow up date etc.

#### 5.3.3 Analysis of the Secondary Endpoints

The secondary endpoints will be evaluated as follows:

#### 5.3.3.1 Proportion of participants with mUFC ≤ ULN at weeks 24, 36 and every 12 weeks thereafter

The number and proportion of participants with mUFC ≤ ULN at 24, 36 and every 12 weeks thereafter will be summarized descriptively along with associated 95% CI.

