LINC-4 was a multinational phase III study of osilodrostat which assessed 73 adults with CD, with an upfront 12-week randomised, double-blind, placebo-controlled period followed by 36 weeks of open-label treatment. The LINC-4 study demonstrated that about 9 times more patients treated with osilodrostat (77%) compared with placebo (8%) achieved mUFC ≤ upper limit of normal (ULN) at Week 12 (OR 43.4; 95% CI 7.1-343.2; P<0.0001). The study showed that 80.8% of patients − including both patients initially randomised to osilodrostat or to placebo and then switched to active osilodrostat at Week 12 - had normal mUFC at week 36 with a maintained benefit at the end of treatment. During the overall study period, the most common AEs reported were consistent with the ones reported in LINC3 with the exception of adrenal insufficiency that was less frequently observed in LINC4 than in LINC3. The most common AEs were arthralgia, decreased appetite, nausea, and fatigue (Gadelha et al. 2022).

Additionally, a phase II, single-arm, open-label, dose-titration, multicentre study (Tanaka et al. 2020) evaluating osilodrostat in Japanese patients with non-CD CS, demonstrated a reduction in mUFC in all patients with endogenous CS other than CD, regardless of disease type with a safety profile that was consistent with that reported previously in CD patients. Of the nine patients enrolled in the study, seven completed the 12-week core treatment period and two discontinued at or prior to Week 12 due to AEs. Of the seven patients who completed 12 weeks of study treatment, two completed 48 weeks of study treatment. Median osilodrostat exposure was 12 weeks. Median (range) average dose including dose interruption (0 mg/day) was 2.143 (1.16–7.54) mg/day. Median (range, population) percentage change in mUFC was −94.47% (−99.0% to −52.6%, n=7) at Week 12. At Week 12, 6/9 patients were complete responders (mUFC ≤ULN) and 1/9 was a partial responder (mUFC >ULN but decreased by ≥50% from baseline). Most frequent AEs were adrenal insufficiency (n=7), gamma-glutamyl transferase increase, malaise, and nasopharyngitis (n=3 each). Serious AEs were seen in four patients. No deaths occurred in this study.

Proven clinical evidence from such previous studies (Pivonello et al. 2020; Gadelha et al. 2022) have made osilodrostat an effective orphan medicine with regulatory approval of its use in Europe and Japan for the treatment of endogenous CS and in the US for CD.

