7 RESEARCH QUESTION AND OBJECTIVES, ENDPOINTS, AND VARIABLES

The proposed study will address the following questions:

The overall objectives of this study are to retrospectively evaluate the safety and effectiveness of osilodrostat in the treatment of non-CD CS in France and to characterise clinical parameters of CS patients treated with osilodrostat.

The proposed study will address the following research questions:

- What are the safety and effectiveness of osilodrostat in the management of non-CD CS patients in a real-world setting?
- What is the cohort demography, and how do clinical characteristics change with osilodrostat treatment?
- How is osilodrostat dosed and titrated in this patient cohort?
- What are the outcomes in these patients, including long term?
- How are these patients monitored (i.e., biochemically, and follow up characteristics)?
- What is the incidence of overall treatment-emergent adverse events (TEAEs) and adverse events of special interest (AESI)?

Table 1 Design Elements

	Objective	Endpoint	Variable
Primary	To estimate the	Number and Proportion of	Mean Urinary free
	effectiveness of	patients with mean urinary	cortisol (mUFC)
	osilodrostat in	free cortisol (mUFC)	
	the treatment of	≤upper limit of normal	
	non-CD	(ULN) at 12 weeks	
	Cushing's		
	Syndrome (CS)		

LCI699-RECAG-NI-059	96
•	

	Objective	Endpoint	Variable
Secondary Secondary	To assess the long-term effects of osilodrostat in the treatment of non-CD Cushing's Syndrome (CS) To assess the	Proportion of patients with mUFC ≤ ULN at weeks 24, 36 and every 12 weeks thereafter. Change from baseline for	mUFC mUFC; morning serum
Secondary	change in biochemical variables associated with osilodrostat treatment in non-CD CS patients	biochemical variables to Week 4, 8, 12, 18, 24, 36, and to every 12 weeks until the earlier of loss to follow-up, death, or the end of the retrospective follow-up period or treatment discontinuation	cortisol (normal and abnormal values as per standard definition)

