8.7.8 Analysis of Primary Endpoint

The number and proportion of patients with mean urinary free cortisol (mUFC) ≤ULN at 12 weeks will be summarised descriptively along with associated 95% CI. It is a fixed value, which is upper limit of normal range. The patients who discontinued treatment prior to 12 weeks for any reason or were lost-to-follow up will be considered non-responders for the primary endpoint. The patients who started treatment with osilodrostat less than 12 weeks prior to the end of the abstraction period, and are still treated with osilodrostat at the end of the abstraction period will be excluded from the analysis.

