#### 5.2 General Presentation Considerations

All report outputs will be produced using SAS® version 9.4 or a later version in a secure and validated environment. All report outputs will be provided to the Sponsor in a single Microsoft Word document. Medical history, procedural/surgical history, and Adverse Events (AE) will be coded using the current version of the Medical Dictionary for Regulatory Activities (MedDRA). The frequency count and percentage of participants will be summarized according to the coded terms of system organ class (SOC) and preferred term. Participant-wise data listing will be provided.

Using the World Health Organization Drug Dictionary (WHO DD), prior and concomitant medications will be tabulated by drug classification, preferred drug name and study group.

Continuous data will be summarized in terms of the descriptive statistics, number of observations (n), mean and SE of mean or 95% CI of mean (as appropriate), SD, median and associated 95% CI of median (as appropriate), minimum, and maximum, unless otherwise stated.

Continuous data that are expected to be skewed and will be presented in terms of the maximum, upper quartile, median, lower quartile, minimum and number of observations. The mean, median will be reported to one more decimal place than the raw data recorded in the database. The SD will be reported to two more decimal places than the raw data recorded in the database. In general, the maximum number of decimal places reported shall be four for any summary statistic.

Project Document Version No.: 4.0; Document Effective Date: 30 October 2023

CONFIDENTIAL

Page 18 of 31

TP-GDO-WW-096-09 Effective Date: 22 Dec 21

Related to: SOP-GDO-WW-019

Categorical data will be summarized in terms of the number of participants providing data at the relevant time point (N), frequency counts and percentages.

Time to event endpoints will be summarized in terms of participants providing data, median and quartiles and represented graphically by Kaplan-Meier curves.

Percentages will be presented to one decimal place. Percentages will not be presented for zero counts. Percentages will be calculated using N as the denominator.

Changes from baseline in categorical data will be summarized using shift tables where appropriate.

Confidence intervals will be presented to one more decimal place than the raw data.

95% confidence intervals for proportions will be calculated using the exact (Clopper-Pearson) method, unless stated otherwise.

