#### 5.11 Handling of Missing and Uninterpretable Data

#### 5.11.1 Missing data

Based on the nature of the study (observational, non-comparative, retrospective), missing data will not be replaced in the statistical analysis of primary and secondary endpoints.

If there is a significant number of missing values for a subject (or if there is confirmed data appearing spurious), a decision will be made following consultation with the sponsor regarding the handling of these data in summaries, prior to DB lock.

Project Document Version No.: 4.0; Document Effective Date: 30 October 2023

CONFIDENTIAL

Only missing dates will be imputed where applicable and the imputation rule corresponding to missing date is given in section 5.10.2 below.

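### The long-term mUFC response rates (Week 24 onward) have no stated denominator and no rule for patients who stop, die or are lost, and the SAP and protocol defaults push the result in opposite directions.

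*SAP*

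**What the plan says.** **The endpoint.** Protocol section 7 asks "What are the outcomes in these patients, including long term", and its Table 1 lists the proportion with mUFC ≤ ULN at Weeks 24, 36 and every 12 weeks thereafter as the endpoint for the long-term objective. The whole analysis text is the sentence in SAP 5.3.3.1: "The number and proportion of participants with mUFC ≤ ULN at 24, 36 and every 12 weeks thereafter will be summarized descriptively", with a 95% CI. SAP 3.6.2(a) adds only when follow-up ends.

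**The Week 12 rule.** Protocol 8.7.8 reads: "The patients who discontinued treatment prior to 12 weeks for any reason or were lost-to-follow up will be considered" non-responders for the primary endpoint. SAP 5.3.2 has the same scope: these patients "will be considered non-responders for the primary endpoint". Protocol 8.1 and SAP section 3 repeat it with the same limit. The modified ITT variant in SAP 5.3.2 also concerns Week 12 only.

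**Follow-up and missing data.** SAP section 3 ends follow-up at the earliest of loss, death, end of the retrospective period or treatment discontinuation. SAP 5.11.1 says that "missing data will not be replaced in the statistical analysis of primary and secondary endpoints".

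**Denominators.** SAP 5.2 defines N by visit: "Categorical data will be summarized in terms of the number of participants providing data at the relevant time point (N"). It then makes N the denominator of percentages. Protocol 8.7.2 bases percentages on the safety or ITT population, and Protocol 8.7.3 and SAP 3.3 place all effectiveness analyses on ITT. SAP 5.13 documents no change from the protocol.

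**The concern.** A patient who stops osilodrostat before Week 24 because of failure or toxicity, or who dies, has no later mUFC by design. If that patient also leaves the denominator, each later rate describes a group increasingly selected for tolerating and responding to the drug. A flat or rising series could then read as durable control while many patients had left. Departure is unlikely to be random: Protocol section 6 says that patients with ectopic CS have the worst prognosis.

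The opposite error is also open. If the whole ITT population is the denominator, a patient who started late in 2022 and could not yet have reached a late visit counts as uncontrolled.

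The endpoint answers the long-term objective of a study meant to support an sNDA, and Amendment 1, which added it, was initiated in response to an FDA letter. As the text stands, two programmers could each follow a document faithfully and report very different long-term rates.

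**Working it through.** **Plan's own figure.** There is none to reproduce: the documents give no expected long-term rate, retention or sample-size formula for this study. As a check on the CI method in SAP 5.2 (exact Clopper-Pearson), 93/137 at Week 24 in the phase III study in Cushing's disease (Protocol section 6) gives 67.9% (59.37 to 75.60), which matches the protocol.

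**Step 1: three readings of one dataset.** Study size of about 100 is from Protocol 8.5. The remaining inputs are assumptions: 20 patients administratively censored (not enough potential follow-up), 30 stopped or lost, and 100 − 20 − 30 = 50 measured, with nobody on drug but unmeasured. An on-drug rate of 68%, borrowed from the figure above, gives 0.68 × 50 = 34 at or below ULN.

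| Rule | Calculation | Rate (exact 95% CI) |
|---|---|---|
| SAP 5.2: N = those with data | 34/50 | 68.0% (53.3 to 80.5) |
| Potential follow-up, stops as non-response | 34/(100 − 20) = 34/80 | 42.5% (31.5 to 54.1) |
| Protocol 8.7.2: whole ITT | 34/100 | 34.0% (24.8 to 44.2) |

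**Step 2: sensitivity to attrition.** Suppose nobody is administratively censored and everyone without data has stopped or been lost. With x controlled, n measured and N = 100, the gap is x/n − x/N = (x/n)(1 − n/N), that is, the on-drug rate times the share without data. At about 68% on drug:

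| With data | SAP N | Stops as non-response | Gap (points) |
|---|---|---|---|
| 90 | 61/90 = 67.8% | 61/100 = 61.0% | 6.8 |
| 70 | 48/70 = 68.6% | 48/100 = 48.0% | 20.6 |
| 50 | 34/50 = 68.0% | 34/100 = 34.0% | 34.0 |
| 40 | 27/40 = 67.5% | 27/100 = 27.0% | 40.5 |

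Over the same range of missingness, the gap is 6 to 36 points at a 60% on-drug rate and 8 to 48 points at 80%. The SAP-N rate hardly moves however many patients leave.

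**Step 3: how many could not have reached a late visit.** Assume uniform starts from 5 April 2019 (Protocol 8.5) to 16 December 2022 (Protocol 8.1), which is 1,351 days. The share with potential follow-up to week w is (days from 5 April 2019 to end of follow-up − 7w)/1,351, capped at 1. Neither document gives a calendar end date, so two are assumed.

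| Assumed end | Week 24 | Week 96 | Week 144 |
|---|---|---|---|
| 16 December 2022 | 1,183/1,351 = 88% | 679/1,351 = 50% | 343/1,351 = 25% |
| 24 October 2023 | 100% | 991/1,351 = 73% | 655/1,351 = 48% |

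The whole-ITT denominator therefore does modest or no harm at Week 24 and considerable harm at the late visits.

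**The case against.** **The direction of bias is not fixed.** A reader might infer that the plan certainly reports on-drug rates and so overstates control. The documents do not settle this. SAP 5.3.3.1 names no denominator, Protocol 8.7.2 points to ITT, and a separate on-treatment family in SAP 3.6.3(b) suggests that the secondary analysis was not meant to be on-treatment only. This stands, and it is why the point is a conflict between two rules.

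**The nine-patient study gives no size.** Protocol section 6 reports: "Of the seven patients who completed 12 weeks of study treatment, two completed 48 weeks of study treatment". It is tempting to set 2/2 = 100% against 2/9 = 22%. But the protocol does not say whether those two were controlled at Week 48, or why the other five who completed the 12-week core period did not continue. The contrast shows a mechanism at most.

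**A rise after Week 12 is not shown to be an artefact.** The rules at Week 12 and later differ, so those rates are not like for like. However, the only explicit by-visit mUFC response series, Week 4 to 60 in SAP 5.10, is by subgroup on the modified ITT and On-Treatment populations.

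**Some stops are not failures.** SAP 3.5 names short-term use before surgery as a category. Counting every stop as non-response could understate control. This stands and shapes the fix.

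**Attrition would be partly visible.** The study is descriptive and the endpoint supportive. The plan already provides N per visit, missing-data counts, discontinuation reasons and an mUFC listing with loss-to-follow-up dates. This helps, but no by-visit accounting sits beside the rate, and visibility does not choose a denominator.

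**Conclusion.** The point holds as a specification defect that can mislead on the long-term objective. The non-responder rule stops at Week 12, SAP 5.3.3.1 puts nothing in its place, and the two general denominator rules conflict without a recorded change.

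Under the SAP rule, overstatement of lasting control is probable, on the assumption that most stops and losses are not controlled patients. Under the protocol rule, understatement is possible and grows at late visits. In the illustration the same 34 controlled patients give 68%, 42.5% or 34%. The actual size is unknown because retention, stop reasons and missing mUFC at Week 24 onward are not given.

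**What to change.** In SAP 5.3.3.1:

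1. Make the main estimate at each week the number with mUFC ≤ ULN divided by ITT patients whose start date gives potential follow-up to that week. State the end-of-abstraction date used.
2. Count discontinuation, loss to follow-up or death before that week as non-response, as at Week 12. Name death explicitly, since the Week 12 text covers it only by implication.
3. State how patients on drug with no mUFC in the window count.
4. State which end-of-treatment imputation in SAP 5.9.5 (A or B) defines a stop. That section reports a high rate of missing end dates, and A leaves some missing.
5. Show the data-only rate beside the main one, labelled as among patients still on osilodrostat with a measurement.
6. Print counts by visit: potential follow-up, on drug and measured, on drug and not measured, stopped by reason (including after surgery), dead, lost, administratively censored.
7. Add a supportive version that reports stops after surgery separately.

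Reconcile Protocol 8.7.2 with SAP 5.2, and record the outcome in SAP 5.13.

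**Cost.** SAP wording and reprogramming of one table family, plus work to settle missing end dates; no new type of data is needed. The long-term rates will look less favourable than data-only rates, and may understate control where stopping was not drug failure. The split by reason makes that visible.

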#### 5.3.3.2 Changes from baseline for biochemical variables and clinical outcomes

For changes from baseline for mUFC and morning serum cortisol to Week 4, 8, 12, 18, 24, 36, and to every 12 weeks until the earlier of loss to follow-up, death, or the end of the retrospective follow-up period or treatment discontinuation, descriptive summaries will be provided.

A participant level listing of biochemical variables and clinical outcomes will be provided as per the data collected in eCRF.

#### 5.3.3.3 Changes from baseline for cortisol expressed as n-fold the ULN

For the mUFC will be calculated the ratio of the value divided by the ULN and calculated as change form baseline and reports as n-fold.

This will be applied also to salivary and morning serum cortisol.

For changes from baseline for cortisol to Week 4, 8, 12, 18, 24, 36, and to every 12 weeks until the earlier of loss to follow-up, death, or the end of the retrospective follow-up period or treatment discontinuation, descriptive summaries will be provided.

# 5.3.3.4 Actual and percent change in BMI, ECG, blood pressure, metabolic, biochemical, and hormone levels from baseline for clinical outcomes

The following variables will be summarized and provided as listing:

BMI, ECG, Blood pressure, CS-specific physical exam findings, Laboratory abnormalities (sodium, potassium, calcium levels, CO2, glucose, Glycated haemoglobin (HBA1c), and hormones (including Plasma ACTH, Serum 11-Deoxycortisol, Plasma 11-Deoxycorticosterone, Plasma Aldosterone, Plasma Renin, Total Serum Testosterone or oestradiol per participant sex, Serum LH, Serum FSH)

For observed values and changes from baseline for above variables to Week 4, 8, 12, 18, 24, 36, and to every 12 weeks until the earlier of loss to follow-up, death, or the end of the retrospective follow-up period or treatment discontinuation, descriptive summaries will be provided.

Project Document Version No.: 4.0; Document Effective Date: 30 October 2023

CONFIDENTIAL

#### 5.3.3.5 Change from initial dose

The osilodrostat dose and change from initial dose by visits will be summarized using descriptive statistics and displayed graphically.

The actual and planned osilodrostat doses administered and reason for dose change will be listed with UFC information.

#### 5.3.3.6 Partial responder

A partial responder is defined as a participant with 50% reduction from baseline, but still >ULN for measures of cortisol levels.

The number and proportion of partial responders at Week 4, 8, 12, 18, 24, 36, and to every 12 weeks thereafter will be summarized descriptively along with associated 95% CI.

This will be reported for mUFC, salivary cortisol and morning serum cortisol as well as the combination of the 3 measures (any of the measures and reported as "Cortisol").

# 5.3.3.7 Complete or partial responder

The number and proportion of complete or partial responders at Week 4, 8, 12, 18, 24, 36, and to every 12 weeks thereafter will be summarized descriptively along with associated 95% CI.

This will be reported for mUFC, salivary cortisol and morning serum cortisol as well as the combination of the 3 measures (any of the measures and reported as "Cortisol").

#### 5.3.3.8 Normalization

The number and proportion of participants with salivary cortisol ≤ ULN at Week 4, 8, 12, 18, 24, 36, and to every 12 weeks until the earlier of loss to follow-up, death, or the end of the retrospective follow-up period or treatment discontinuation, will be summarized descriptively along with associated 95% CI. This will be applied also to morning serum cortisol.

Normalization will be evaluated also as frequency of participants with at least 50% of the measures ≤ ULN.

This will be reported for mUFC, salivary cortisol and morning serum cortisol as well as the combination of the 3 measures (any of the measures and reported as "Cortisol").

